### 5.4 Secondary Outcomes

Secondary outcomes of parental, clinical and financial importance have been identified. Data relating to maternal or neonatal readmission to hospital within seven days of birth is already reported by community midwives and captured in EuroKing® systems at the point of discharge from midwifery care. Data relating to some primary and secondary outcomes are not currently captured in EuroKing® maternity information systems and at site opening the EuroKing® E3 systems at sites will be amended to prospectively collect these data.

Maternal secondary outcomes: Maternal Intrapartum: Shoulder dystocia and required management, management of the third stage of labour, need and reason for obstetric involvement in woman's care including sepsis; mode of birth, maternal position at birth, treatment for haemorrhage, incidence and management of perineal and other genital trauma. Maternal Postnatal: duration of postnatal stay, breast feeding initiation and continuation, higher level care, and maternal readmission to hospital within seven days of birth.

Infant secondary outcomes: Snapped umbilical cord prior to clamping, skin to skin contact at birth, timing of cord clamping, resuscitation, Apgar scores, administration and duration of intravenous antibiotics. Incidence of: lumbar puncture, culture proven infection, brachial plexus injury; treatment for jaundice; readmission to hospital within seven days of birth; therapeutic hypothermia;

TPL/003/2 v1.0

Page **15** of **38** 

neonatal unit admission and duration; cause of neonatal death; respiratory support. Where available, and where the risk status and pool usage of mothers can be determined, retrospective data will be used in addition to prospective data, to describe the occurrence of these infant outcomes.

Additional data items with accompanying background development required to fully answer the research aims will be added to E3 systems at study sites, and will include:

- Maternal risk factors at pool entry
- Maternal risk factors developing during labour
- Time of entry into pool
- Time of last leaving pool
- Reason for leaving pool if prior to birth
- Partial birth in water (breech / shoulder dystocia)
- Birth position in pool
- Conversion from planned physiological to active third stage labour management.
- Delivery of placenta in or out of water
- Treatment for haemorrhage
- Reason for obstetric involvement in woman's care

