#### 9.6 Cohort Study Statistical considerations

#### 9.6.1 Sample size

The non-inferiority of birth in water compared to birth on land on rates of OASIS will be examined by parity. The Birthplace in England study found that overall 4.6% and 1.6% of nulliparous and parous women respectively, sustained OASIS. A sample size of 15,000 nulliparous and 15,000 parous 'low risk' women (7,500 each water and land) is required to obtain 90% power, and a 95% one-sided confidence interval around a treatment difference of zero. A non-inferiority margin of 1% or less,

Page **22** of **38** 

and 0.6% or less will be taken as clinically non-significant amongst nulliparous and parous 'low risk' women respectively. Since nulliparous women birthing in water are regarded as the least prevalent of the four groups, a data collection period providing data on 7,500 would ensure adequate numbers in the other three, more prevalent groups. These data will be combined to assess the effects averaged across both strata at an increased power, with a combined required sample size of 30,000 'low risk' women. We have assumed that 25% of the 6,600 waterbirths recorded in EuroKing® in 2015 were nulliparous women (1650/annum). Allowing for staggered site set-up, five years of combined retrospective and prospective data collection would be required (January 2015 – November 2020). The exact ratio of nulliparous and parous women who give birth in water will be determined once the retrospective data are examined, but with increasing numbers of waterbirths, with 18 of the 35 EuroKing® using sites, collectively undertaking 6,037 waterbirths in 2016, we are confident the study will have sufficient power to answer this important clinical question.

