For the neonatal primary outcome, an estimate of 5% is used for the proportion of babies born to 'low risk' mothers experiencing 'adverse neonatal outcome or treatment'. A non-inferiority margin of 1.0% or less will be taken as clinically non-significant. A sample size of 16,200 babies (8,100 per group water / land) are required to have 90% power, and a 95% one sided confidence interval around a treatment difference of zero. The identification of women who leave and do not leave the pool prior to delivery of the placenta can only be captured by addition of new data items in the prospective cohort. As delivery of placenta in water, or postpartum haemorrhage of >1,000 ml following waterbirth are relatively uncommon events (17% and 1% respectively) the proposed sample size of 30,000 women who use a birth pool will be underpowered to detect a difference in these outcomes, but will be described.

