#### 9.6.5 Primary analysis

The primary analyses are based on a non-inferiority test of birth in water versus on land, comparing 1) the proportion of mothers that have OASIS, and 2)the proportion of babies with a composite outcome of 'adverse neonatal outcome or treatment'.

To test the primary hypothesis of non-inferiority between birth in water and on land, the two outcomes will be evaluated for non-inferiority using logistic regression models, in the first instance with no adjustment for covariates. Adjusting for potential confounders may result in a more precise treatment effect estimate. The potential confounders of both primary outcomes (listed in table 1) will be considered and the impact on bias through conditional associations when conditioning on these covariates will be assessed using directed acyclic graphs (DAGs). The main logistic model will incorporate these selected covariates through regression adjustment. Results will be reported as an (unadjusted) odds ratio (birth in water compared to on land), and a two-sided 90% confidence interval (CI) for the (unadjusted and adjusted) odds ratio will be calculated. Non-inferiority will be concluded if the upper limit of the 90% CI for the difference in neonatal outcome between the groups is less than 1.0% (OR<1.21). Similarly, for the mother's outcome, non-inferiority will be concluded if the upper limit of the 90% CI for the difference in the proportion of OASIS between the groups is less than 1.0% (OR<1.23) in nulliparous 'low-risk' women and less than 0.6% (OR<1.38) in parous 'low-risk' women. The data will then be combined to assess the effects averaged across both strata.

If non-inferiority is shown, then a superiority analysis will be conducted as a secondary analysis of the primary outcomes using logistic regression and will be presented as an (unadjusted and adjusted) odds ratio of outcomes in the waterbirth group compared with the birth on land group. Parameter estimates will be provided alongside 95% CI and p-value. Secondary outcomes will have non-inferiority testing as detailed above.

	Maternal	Adverse neonatal
	outcome: OASIS	composite outcome
Maternal age (years)	√	$\checkmark$
Maternal BMI	✓	
Parity	√	
Duration of labour	✓	
Gestational age at delivery (weeks)	√	$\checkmark$
Child birth weight (g)	✓	$\checkmark$
Child head circumference (cms)	√	
Maternal thyroid disease (including hypothyroidism)		$\checkmark$
Pre-labour ruptured membranes		$\checkmark$

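### The non-inferiority rule set for the primary outcomes is carried over to every secondary outcome, where its two scales disagree, its direction is sometimes wrong, and for some outcomes it is undefined

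*Protocol*

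**What the plan says.** Section 9.6.5 sets the decision rule for the two primary outcomes. The neonatal composite is non-inferior if the "upper limit of the 90% CI for the difference in neonatal outcome between the groups is less than 1.0% (OR<1.21"), and OASIS if the corresponding limit is "less than 1.0% (OR<1.23) in nulliparous 'low-risk' women and less than 0.6% (OR<1.38) in parous 'low-risk' women". The same section specifies logistic regression, with a two-sided 90% interval for the odds ratio. It ends its text on hypothesis testing with: "Secondary outcomes will have non-inferiority testing as detailed above". No other margin appears in the protocol, and the sentence does not say which of the three carries over, on which scale, or in which direction.

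The secondary list in section 5.4 is mixed. Maternal items include "Maternal Postnatal: duration of postnatal stay, breast feeding initiation and continuation, higher level care", as well as shoulder dystocia, maternal position at birth and third-stage management. Infant items include brachial plexus injury, therapeutic hypothermia, snapped cord, skin to skin contact, Apgar scores, length of neonatal unit stay and cause of neonatal death.

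**The concern.** A non-inferiority margin has meaning only for a given outcome, at a given reference rate and in a given direction. The protocol's margins were chosen for three outcome-by-group rates between 1.6% and 5%. Carried over to the section 5.4 list, they meet harms that may be far rarer, outcomes where a higher value is better, and outcomes that are not yes/no events.

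The study aims to say whether waterbirth is as safe as leaving the pool, and section 3.1 expects the findings to reach pregnant women quickly. A formal non-inferiority label on a rare neonatal harm, or a failure to earn that label, would be read as a safety statement. Neither should depend on a margin that was not chosen for that outcome.

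**Working it through.** **Inputs from the protocol.** OASIS: "overall 4.6% and 1.6% of nulliparous and parous women respectively, sustained OASIS". Neonatal composite: "an estimate of 5% is used for the proportion of babies born to 'low risk' mothers". Error level: "a 95% one-sided confidence interval around a treatment difference of zero", so z = 1.645. Power 90%, so z = 1.282. Group sizes: 7,500 per group in each parity stratum for OASIS (15,000 per group combined) and 8,100 per group for the neonatal composite.

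**Assumed.** Land rates of 0.1% and 0.5% for rare harms, because the protocol gives none. Also 1%, borrowed from section 9.6.1, where it is the rate of haemorrhage above 1,000 ml after waterbirth; its use as a land rate is illustrative only.

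**1. Reproduce the design.** n per group = (1.645 + 1.282)² × 2p(1−p)/margin².
- p = 4.6%, margin 1.0 point: 7,517 (stated 7,500)
- p = 1.6%, margin 0.6 point: 7,491 (stated 7,500)
- p = 5%, margin 1.0 point: 8,136 (stated 8,100)

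The margins, rates and error level are therefore read as intended.

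**2. Where the bracketed odds ratios come from.** OR = odds(p + margin)/odds(p).
- 5% to 6%: 1.213
- 4.6% to 5.6%: 1.230
- 1.6% to 2.2%: 1.383

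Away from those rates the match is lost. OR 1.21 corresponds to +0.99 point at 5%, +0.21 point at 1% and +0.02 point at 0.1%.

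**3. Rare harms on the difference scale.** With land rate p and n = 8,100, find the true waterbirth rate q that passes with 90% probability: Φ[(margin − (q − p))/√(p(1−p)/n + q(1−q)/n) − 1.645] = 0.90.

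| Land rate | Increase allowed by 1.0 point | q at 1.0 point | q/p at 1.0 point | q/p at 0.6 point |
|---|---|---|---|---|
| 0.1% | 11-fold | 0.79% | 7.9 | 4.6 |
| 0.5% | 3-fold | 1.09% | 2.2 | 1.5 |
| 1% | 2-fold | 1.49% | 1.5 | 1.1 |

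A larger sample does not cure this. At 15,000 per group the 1.0-point ratios become 8.7, 2.4 and 1.6.

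**4. Rare harms on the odds-ratio scale.** Power with truly equal rates = Φ[ln(limit)/√(2/(n p(1−p))) − 1.645].

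| Land rate | OR<1.21, n = 8,100 | OR<1.21, n = 15,000 | OR<1.38, n = 8,100 |
|---|---|---|---|
| 0.1% | 10% | 13% | 16% |
| 0.5% | 21% | 32% | 42% |
| 1% | 33% | 50% | 65% |

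**5. Direction.** Assume 80% breast feeding on land and 15,000 per group.
- Fall to 70%: standard error √(0.8×0.2/15,000 + 0.7×0.3/15,000) = 0.00497. The upper limit is −0.100 + 1.645 × 0.00497 = −9.2 points, so the loss passes.
- Rise to 85%: standard error 0.00438. The upper limit is +0.050 + 1.645 × 0.00438 = +5.7 points, so the gain fails.
- The odds-ratio scale gives the same answers. The fall has OR (0.7/0.3)/(0.8/0.2) = 0.58, upper limit about 0.61, and passes. The rise has OR 1.42, already above 1.21, and fails.

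**6. Outcomes that are not yes/no.** For lengths of stay, neither a margin in percentage points nor an odds ratio from a logistic model is defined. Position at birth and cause of neonatal death have no better or worse direction on which to build the test.

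**The case against.** The best defence is that the sentence refers only to the method (a logistic model and a 90% interval). Section 9.6.5 ties each margin by name to one outcome, literal carry-over to maternal position would make no sense, and margins for secondary outcomes may be set in the SAP, which is not shown. This is a fair account of what the authors may have meant, but it does not rescue the sentence. A non-inferiority test needs a margin, none other is stated, and where the protocol wants to defer to the SAP it says so, as in section 9.6.2 on missing data.

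Other objections stand and limit the point:
- A reader might infer that the plan would certainly declare many-fold increases in rare harms non-inferior. That holds only on the difference scale and only at assumed rates below about 0.5%. The odds-ratio limits in the same sentences reverse it.
- A reader might equally infer that the odds-ratio limit makes failure near certain whatever the truth. Power of 21% to 33% at rates of 0.5% to 1% is poor but not nil. It is higher with 15,000 per group or OR<1.38, and would be higher still if waterbirth truly lowered the rate. Section 7 also allows retrospective data to add power for secondary neonatal outcomes.
- The protocol is cautious elsewhere. Section 5.3 accepts that single components of the composite are too infrequent to detect differences, and sections 9.6.1 and 9.6.6 say the haemorrhage comparison by placental delivery will only be described. That caution sits badly with blanket testing of secondary outcomes.
- Non-inferiority for some secondary safety outcomes fits the study's aim, so a complete ban is not needed.

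**Conclusion.** The sentence is wrong as written. It applies one rule to all secondary outcomes, and that rule's two scales agree only at event rates of 5%, 4.6% and 1.6%. For rarer harms it is too lax on the difference scale or largely unattainable on OR<1.21, and the protocol does not say which scale governs. At the one low harm rate the protocol gives (1%), the 1.0-point margin is a doubling; larger multiples rest on assumed rates. The wrong direction for beneficial outcomes and the lack of definition for durations do not depend on any assumed rate; the 80%, 70% and 85% above only illustrate the former.

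It would be tempting to treat this as a threat to the main result. The documents do not support that: the primary outcomes, their margins, the sample sizes and the primary conclusions are untouched. It should be fixed, at moderate severity.

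**What to change.** Replace the sentence in section 9.6.5 with: *Secondary outcomes will be reported as effect estimates with confidence intervals; no non-inferiority conclusion will be drawn unless a margin, scale and direction for that outcome have been prespecified.* If the sponsor wants non-inferiority for a few secondary safety outcomes, list them with those three items each, and code any outcome where higher is better as its failure (for example, not breast feeding).

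The cost is a change of wording, plus a matching check of the SAP, and the loss of secondary non-inferiority claims that have no margin of their own. Data collection, sample size and the primary analyses do not change.

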#### Table 1. Potential confounders for both maternal and baby outcomes

#### 9.6.6 Subgroup analysis

Maternal: A planned and powered sub group of the primary maternal outcome will be conducted to compare rates separately for primiparous and multiparous women. One previous cohort study of women using a pool during labour found that delivery of placenta in water and postpartum haemorrhage of >1,000 ml to be relatively uncommon (17% and 1% respectively). It is likely therefore that the proposed sample of 15,000 women who will give birth in a pool during the period of prospective data collection (2018 – 2020) will be underpowered to detect a difference in rates of postpartum haemorrhage between women who remain in, or leave the pool, for delivery of the placenta, but these data and outcomes will be described. The relationship between the proportion of women using a pool during labour, at individual sites and the incidence of adverse maternal and primary outcomes will be described.

TPL/003/2 v1.0

Page 25 of 38

Neonatal: A planned sub group of the primary neonatal composite outcome will also be conducted to compare rates separately for babies born to primiparous and multiparous women.

#### 15.3 Sensitivity analysis

For both primary outcomes a number of sensitivity analyses will be performed to assess the robustness of the results to factors which may introduce bias.

Propensity score analysis: whether a woman who uses water immersion during labour remains in the pool for birth is likely to be influenced by their age, parity and other characteristics. This will result in imbalanced comparison groups. Incorporating propensity scores, i.e. the 'propensity' of a woman to choose a waterbirth, in the analysis is a way of controlling for this bias. It also allows a more detailed examination of the impact of imbalanced comparison groups on the results. Differences in baseline characteristics before and after propensity score matching will be examined and analyses re-run.

Instrumental variable analysis: Instrumental variables (IV) are factors associated with outcomes only via their association with exposure (in this case to birthing in water) and are independent of other factors associated with exposure. IVs can deal with the unobserved factors in selection bias and can add potential value to a study dealing with just observable factors. Such variables might include midwifery practice, or other factor that encapsulates unit culture. The capture of denominator data to provide information on the proportion of women using water for labour or birth at each unit, and the qualitative component of the study, will be utilised in this analysis.

### **10** Qualitative Component

The qualitative component of the study will explore the influence of maternity unit culture on waterbirth and by placing the findings in the context of current NHS service provision will assist interpretation of the study's findings. Professional attitudes to waterbirth vary widely, with strong views held. It is therefore likely that aspects of unit culture may influence waterbirth rates. For example, differing professional perspectives may act as barriers or facilitators to birth in water, as may unit configuration and model of care (i.e. consultant-led or midwife-led), level of complexity of obstetric care provided, birth environment and facilities, staff training, local policies and procedures. There is currently no robust evidence describing these possible influencing factors.

The qualitative component will use a two-stage approach to identify and explore the influence of cultural factors, through collection and analysis of group and one-to-one interviews with a range of professional and lay stakeholders.

The key research questions are:

Page 26 of 38

- What factors influence birth pool use in units with high and low waterbirth rates?
- What factors influence giving birth in water in units with high and low waterbirth rates?

The term 'unit' refers to all births taking place within the NHS Trust or Health Board, whether within an institution or at home.

The qualitative component design is informed by Realistic Evaluation, an approach which is wellsuited for unpacking the causal web of factors that may affect a complex intervention such as waterbirth. We will seek to identify 'what works in which circumstances and for whom' in relation to waterbirth. Stage one will focus on engaging with key senior professional stakeholders to hypothesise the generative mechanisms that explain how outcomes arise (i.e. the extent of pool use and waterbirth) and how these may be influenced by context. In stage two, these hypotheses will be tested in four case study sites, using the generative mechanisms and contextual factors identified in stage one to inform the development of interview and focus group schedules. Organisational case studies have been used to add a valuable qualitative component to other recent large-scale birth studies, for example within the Birthplace in England study. By exploring organisational culture, insights can be gained into the effect of context on professional practice and service user experiences.

#### 10.1 Qualitative component stage one

**Design:** Six closed online stakeholder discussion groups will be conducted, hosted on the Cardiff University website.

Participants: Proposed groups are:

- 1. Heads of Midwifery / Midwifery Managers from study sites.
- 2. Consultant Midwives from study sites.
- 3. Band 5 / 6 clinically focused midwives.
- 4. UK Obstetricians from within and outside of study sites (accessed via RCOG or another route).
- 5. UK Neonatologists from within and outside of study sites (accessed via the UK Neonatal Collaborative (UKNC) the RCPCH or another route.
- 6. Public including members of the RCOG Women's group, with participation open to women at study and non-study sites.

**Participant Identification:** Prospective participants will be recruited though various routes including potentially: participating units, professional and lay networks including social media, Royal Colleges. Those expressing interest will be provided with an electronic PIS explaining what participation will entail and what measures will be taken to protect their identity. Participation in the discussion will be taken as consent.

**Online discussion group:** Ground rules will be in place to ensure that the identity of individuals, departments or organisations are not disclosed and that participants act respectfully online. The groups will be administered and moderated by members of the research team, with access restricted to participants and the research team. Participants will be asked to discuss what cultural factors, in their experience, might contribute to the high and low rates of pool use and waterbirth. **Analysis:** Framework analysis will be undertaken to generate key hypotheses for further exploration in stage two.

### 10.2 Qualitative component stage two

**Design:** In-depth organisational case studies will be conducted in four sites. The retrospective data extracted on site opening will be analysed to identify the range of the proportions of women using a pool for labour and birth. The four sites will be purposively sampled to represent sites with either high or low waterbirth rates.

**Sites:** The number of sites and time-frame is pragmatic; purposive site selection should provide breadth and depth of investigation within the resources and time available. To answer the qualitative research questions and address the secondary objectives of the study, it is proposed that the case studies be configured as follows:

- SITE A Obstetric Unit. High waterbirth rate;
- SITE B Obstetric Unit. Low waterbirth rate (excluding obstetric units without a bath or pool);
- SITE C Midwifery Unit. High waterbirth rate;
- SITE D Midwifery Unit. Low waterbirth rate, (excluding midwifery units without a bath or pool).

**Data Collection:** The aim of stage two is to explore the interplay between the generative mechanisms identified in stage one, organisational context and proportions of women that use water immersion for labour or birth. In each site, the following data will be collected:

1. Key documents relating to pool use and waterbirth (e.g. Guidelines, protocols, user information leaflets)

- Three audio-recorded focus groups constituted as follows: i) Band 5 & 6 Midwives, ii) Band 7 Midwives, iii) Lay members of the local Maternity Voices / Maternity Services Liaison Committee.
- 3. Up to eight audio-recorded semi-structured interviews with key local stakeholders of which at least three will be with lay representatives. Key local stakeholders include: Head of Midwifery, Consultant Midwife, obstetricians, neonatologists, lay representatives from Maternity Voices / Maternity Services Liaison Committee, NCT or other local lay groups.

**Sampling:** Sampling will be purposive, to ensure a range of views are gathered from those with relevant experience.

Interviews: Interviews will be conducted face to face or by phone.

**Participant identification:** The study will be publicised at unit meetings and via local networks and potential participants requested to contact the research team or sign up to receive information. Prospective participants will be provided with participant information sheets and consent forms and invited to take part.

**Analysis:** Data will be thematically analysed initially, supported by NVIVO, in order to develop an analytic framework, which will then be used to code all data.

